5.1. Definition of analysis sets

Screened set (SCR)

The screened set is defined as all subjects who signed informed consent.

Safety set (SAF)

The safety set is defined as all subjects who received at least one dose of investigational medicinal product (IMP).

Safety boost set (SAFB)

The safety boost set is defined as all subjects who received two doses of IMP (first injection (Dose 1) and second injection (Dose 2)).

Note: Group A will be excluded from the SAFB as they receive only a single injection according to protocol.

Immunogenicity set (IMM)

The immunogenicity set is defined as all subjects who received at least one dose of IMP and have at least one post-baseline functional antibody titer (e.g., VNT or an equivalent assay) immunogenicity assessment.

Note: The expression 'have at least one post-baseline functional antibody titer immunogenicity assessment' refers to having either at least one post-baseline neutralizing antibody titer or one post-baseline ELISA titer immunogenicity assessment.

Immunogenicity per-protocol set (IMMPP)

The immunogenicity per-protocol set is defined as all subjects included in the immunogenicity set that have no major protocol deviations as determined by the clinician and who received two doses of IMP (first injection (Dose 1) (for Group A and B) and second injection (Dose 2) (only for Group B)).

Note: Subjects with any major protocol deviation thought to interfere with either the mechanism of action or immunogenicity test measurements will be excluded from IMMPP set.

Note: The definitions of all analysis sets apply within the BNT162-14 trial. In all analysis sets, subjects will be assigned to the treatment groups (i.e., vaccine type) according to the actual treatment they received ("as treated"). The condition of receiving two doses of IMP will not apply to Group A.

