6.1.1. Tables and listings

Tables

In general, data will be summarized as follows:

- Group A by vaccine [Comirnaty[®], BNT162b2s01], and total
- Group A subjects having received Comirnaty[®] by HIV infection status
- Group A subjects having received BNT162b2s01 by HIV infection status
- Group B by transplant status, and total
- Group B immunology subset by transplant status, and total

Descriptive summary tables and figures will be based on scheduled visits.

Continuous variables will be summarized using the following descriptive statistics: number of subjects with non-missing data (n), mean, standard deviation (SD), median, minimum (min) and maximum (max).

Descriptive statistics of titer and fold rise of titer will additionally include geometric mean and its two-sided 95% confidence interval (CI). The geometric mean titer (GMT) is calculated as the mean of the logarithm of the functional antibody titers, backtransformed into the original scale. Two-sided CIs will be obtained by calculating CIs using t-distribution for the mean of the logarithmically transformed assay results and transforming the limits back to the original scale.

Geometric mean fold rise (GMFR) is calculated as the mean of the difference of logarithmically transformed assay results (post vaccination time point – pre vaccination time point) and back-transformed into the original scale. Two-sided CIs will be obtained by calculating CIs using Student's t-distribution for the mean difference of the

logarithmically transformed assay results and transforming the limits back to the original scale.

Categorical variables will be summarized presenting absolute and relative frequencies (n and %) of subjects in each category (including the category 'missing' if applicable). Percentages will be calculated based on the number of subjects in the respective analysis set (N) as denominator if not stated differently. Percentages may be presented with exact 95% Clopper-Pearson CIs.

SDs and CIs will only be calculated if values from at least 3 subjects are available.

Listings

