6.4. Primary endpoint analyses

The primary endpoints are solicited local reactions at the injection site occurring up to 7 days after each injection, solicited systemic reactions occurring up to 7 days after each injection, the proportion of subjects with at least one serious adverse event (SAE) occurring up to 26 weeks after the first injection, the proportion of subjects with at least one adverse event of special interest (AESI) occurring up to 26 weeks after the first injection and the proportion of subjects with at least one unsolicited treatment emergent adverse event (TEAE) occurring up to 28 days after each injection.

All primary analyses will be performed using the SAF and analyses of adverse events for Group B will possibly be repeated using the SAFB.

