6.4.1. Solicited local reactions

Definition

Solicited local reactions at the injection site consist of pain, tenderness, erythema/redness, and induration/swelling. These are assessed by the subject in a diary as stated in the protocol Section 8.2.4.

Local reactions will be graded based on the criteria given in the United States (US)Food and Drug Administration (FDA) Guidance for Industry 'Toxicity Grading Scale for Healthy Adult and Adolescent Volunteers Enrolled in Preventive Vaccine Clinical Trials' for 'Local Reaction to Injectable Products'. The grading of local reactions to injectable product is detailed in Section 10.3.2.1 (Table 5) of the protocol. The grades are Grade 1 (mild), Grade 2 (moderate), Grade 3 (severe), and Grade 4 (potentially life threatening).

The solicited local reactions will be evaluated for each injection, i.e.

- First injection (Dose 1) up to day 7 (inclusive) after first injection (Group A, immunology subset of Group B)
- Second injection (Dose 2) up to day 7 (inclusive) after second injection (Dose 2) (immunology subset of Group B)
- Both intervals combined (immunology subset of Group B)

The intervals will start with the date and time of the injection.

Note: The interval 'first injection (Dose 1) up to day 7 after first injection (Dose 1)' includes study day 1 to study day 7. This applies to the other intervals accordingly.

All analyses are based on local reactions independent of their relatedness to IMP.

Analysis

All analyses will only be performed for Group A and immunology subset of Group B.

Local reactions with missing time and occurring on the day of first injection (Dose 1) will be assigned to all intervals starting with the first injection (Dose 1). Local reactions with missing time and occurring on the day of the second injection (Dose 2) will be assigned

to all intervals including the second injection. Local reactions with missing date will be assigned to each of the applicable intervals if it cannot be ruled out, that it belongs to the time interval.

The number and percentage of subjects reporting at least one local reaction in each applicable time interval will be summarized for any local reaction and by worst grade.

The denominator of the percentages will be the number of subjects with any information on local reactions in the diary available in the respective time interval.

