The number and percentage of subjects reporting at least one local reaction will be summarized by local reaction type (pain, tenderness, erythema/redness, and induration/swelling) and by worst grade for each time interval. The denominator of the percentages will be the number of subjects with any information on local reactions in the diary available in the respective time interval. This analysis will be repeated for local reactions of Grade \geq 3.

Additionally, the following analyses will be done for local reactions and for any reaction (local or systemic):

Time after first injection (Dose 1) (Group A and immunology subset of Group B) and after second injection (Dose 2) (immunology subset of Group B) from

- First injection (Dose 1) to first reaction
- First injection (Dose 1) to first reaction of Grade ≥3
- First reaction to last reaction and
- First reaction of Grade \geq 3 to last reaction of Grade \geq 3

will be determined per subject and will be summarized descriptively overall and by local reaction term.

Moreover, the frequency of subjects with any solicited local reactions and solicited reactions within 7 days after each dose per day and the frequency of subjects with solicited local reactions within 7 days after each dose by term per day will be analyzed. This analysis will be analyzed additionally for solicited local reactions of Grade \geq 3.

The compliance with the diary from each injection up to 7 days after each injection will be presented. A table giving the number and percentage of subjects with any information on local reactions in the diary (overall and by local reaction term) available per day will be given. The compliance with the diary based on any information on any reaction (local or systemic) will also be given.

All local reactions from the trial will be listed. Additionally, all days with information on local reactions in the diary will be listed.

For Group A (by randomization) and immunology subset of Group B (by transplant status yes/no), local reactions assessed by subject will be presented graphically using a bar plot. The following plot will be provided:

• Local reactions within 7 days after each dose by worst grade

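### SAP 6.4.1 names no denominator for the per-day solicited-reaction tables, so the default keeps subjects with no diary entry that day, or no Dose 2, in the base

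*SAP*

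**What the plan says.** SAP 6.1.1 sets the general rule: "Percentages will be calculated based on the number of subjects in the respective analysis set (N) as denominator if not stated differently". For the solicited-reaction endpoints, SAP 6.4 names the set: "All primary analyses will be performed using the SAF". SAP 5.1 admits to that set anyone given at least one dose; it requires neither a diary nor a second dose. SAP 6.4.1 then narrows the tables: "All analyses will only be performed for Group A and immunology subset of Group B".

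SAP 6.4.1 departs from the general rule twice, both times for tables over a whole post-injection interval (any local reaction; reaction by type and worst grade). There the base is the "number of subjects with any information on local reactions in the diary available in the respective time interval". The intervals run from the injection to day 7, with a combined interval for the immunology subset.

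A later paragraph of the same section adds "the frequency of subjects with any solicited local reactions and solicited reactions within 7 days after each dose per day", the same by term, and a repeat for Grade 3 or higher. It names no denominator. SAP 6.4.2 applies the local-reaction methods to systemic reactions, so it inherits the gap. The next paragraph of 6.4.1 plans a diary-compliance table that counts subjects with diary information on each day, overall and by term, but does not link it to the daily reaction percentages.

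**The concern.** A solicited reaction can be seen only on a day for which the subject made an entry. A percentage whose numerator comes from that day's entries, and whose denominator is everyone dosed at least once, mixes the reaction rate with the diary-completion rate. If completion differs by day, dose or Group A arm, so does the dilution, and the daily profiles are not comparable.

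The Dose 2 tables have a second, clearer problem. A subject who never received Dose 2 was never at risk of a Dose 2 reaction but stays in the Safety Set. The plan foresees such subjects: SAP 1.2 describes the transplant subjects' second injection as potential and says that those not eligible in the window will not get it in this trial. Protocol 7.1.1 lists reasons for which Group B subjects may stop receiving injections.

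**Working it through.** The plan states no daily percentage and no diary-completion rate, so there is no figure of its own to reproduce. The check is a reading of the rules followed by arithmetic on assumed completion.

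**Which denominator applies.** The default holds unless something else is stated. The two stated exceptions belong to interval tables; the daily paragraph has none. Elsewhere, when an available-data base is wanted, the SAP says so, as for seroconversion in 6.5.3. Following the text therefore gives the Safety Set N in each column.

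**Inputs.** Group A has at most 90 subjects randomized 2:1, so 60 and 30 if full (SAP 1.2). The immunology subset has 129, of whom up to 15 are transplant subjects, leaving 129 − 15 = 114. The completion rates, the reaction rate of about 60% among subjects with an entry, and the Dose 2 drop-off are assumptions.

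**Formula.** With r reactors, E subjects with an entry that day and N in the column:

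r/N = (r/E) × (E/N)

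The relative shortfall is 1 − E/N: 5%, 10%, 15% and 20% at completion of 95%, 90%, 85% and 80%.

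| Column | N | E | r | r/E | r/N |
|---|---|---|---|---|---|
| BNT162b2s01 arm, 5% missing | 60 | 57 | 34 | 59.6% | 56.7% |
| BNT162b2s01 arm, 10% missing | 60 | 54 | 32 | 59.3% | 53.3% |
| BNT162b2s01 arm, 20% missing | 60 | 48 | 29 | 60.4% | 48.3% |
| Comirnaty arm of Group A, 10% missing | 30 | 27 | 16 | 59.3% | 53.3% |
| Non-transplant subset, 10% missing | 114 | 103 | 62 | 60.2% | 54.4% |
| Non-transplant subset, 20% missing | 114 | 91 | 55 | 60.4% | 48.2% |

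**Dose 2, non-transplant subset.** If 5% of 114 never receive Dose 2, 108 do. With every diary complete and 65 reactors, 65/108 = 60.2% is reported as 65/114 = 57.0%. If 10% of the 108 also have no entry, E = 97, and 58/97 = 59.8% is reported as 58/114 = 50.9%.

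**Dose 2, transplant subjects.** Each of 15 without Dose 2 removes 1/15 = 6.7% of the percentage in relative terms; two remove 2/15 = 13.3%.

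**Would the interval denominator serve?** No. If 98% of 60 (59 subjects) have some entry in the interval and 54 have one on the day, 32 reactors give 32/59 = 54.2%, against 32/54 = 59.3%. Subjects with an entry only on other days are still in the base.

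**When the shortfall is a bias.** Let recorders react at rate p and non-recorders at rate q. The true rate is (E/N)p + (1 − E/N)q. Take N = 60, E = 48, p = 60.4%:

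- q = p: truth 60.4%; the default is 12.1 points low and the diary-based figure is right.
- q = p/2 = 30.2%: truth 0.8 × 60.4 + 0.2 × 30.2 = 54.4%; the default is 6.0 points low and the diary-based figure 6.0 points high.
- q = 0: truth 48.3%; the default is right and the diary-based figure 12.1 points high.

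Subjects never given Dose 2 fall outside this argument: they were not at risk and do not belong in a Dose 2 base.

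**The case against.** The strongest defence is that the daily tables are supplementary. The protocol endpoint is reactions up to 7 days after each injection, and the SAP gives those interval summaries a diary-based denominator. The per-day breakdown is an SAP addition, nothing is formally tested, and the planned compliance table and diary listing let a reader rebuild each daily percentage. The sentence also says only frequency; the percentage follows from 6.1.1, which reports categorical data as n and %. All of this stands and limits the weight of the point. None of it supplies the missing denominator.

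Some stronger readings are tempting but unsupported:

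- A reader might infer that subjects without an entry are classified as reaction-free. SAP 6.1.3 handles missing data as missing, and 6.1.1 allows a missing category. The reaction percentage is nevertheless the same while N remains the base.
- A reader might infer that the base is the whole Safety Set. The 459 − 129 = 330 planned Group B subjects outside the immunology subset are not in these tables.
- A reader might infer that the dilution grows over the week and makes reactions look shorter. Neither document gives a completion rate or trend, and duration is summarized separately, per subject, from first to last reaction.
- A reader might expect a corrected daily base to match the interval tables. It will not: a per-day count also differs from an interval count.

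The safety boost set might seem to cover the Dose 2 problem. SAP 6.1.1 and 6.4 foresee its use only for repeating adverse-event analyses, and it would leave missing entries in the base.

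**Conclusion.** The gap is real and narrow. As written, the daily percentages for local and systemic reactions (any, by term, Grade 3 or higher) rest on the Safety Set N of each reported column and equal the diary-based percentage times E/N. At an assumed 95% to 80% completion they are 5% to 20% lower in relative terms. That is a bias of the same size if non-recorders react as often as recorders, and smaller if they react less; with complete diaries it disappears. The Dose 2 tables contain the clearest error, since subjects never given that dose do not belong in the base whatever is assumed about non-recorders; among 15 planned transplant subjects each costs about 7% relative. The interval-level primary summaries and the first-to-last-reaction durations are not affected, so this is a specification fault in a descriptive supplement and does not threaten the primary results.

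**What to change.** Add one sentence to SAP 6.4.1, which 6.4.2 then inherits: for per-day analyses the denominator is the number of subjects who received that dose and have diary information for that reaction type on that day, taken from the per-day diary-compliance table. Print that n beside each percentage, so that completion is visible and readers can judge the assumption about non-recorders. The cost is one sentence and the reuse of a count already planned; no new data, no change to the design or the interval tables, and no clinical decision.

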6.4.2. Solicited systemic reactions

Definition

Solicited systemic reactions consist of vomiting, diarrhea, headache, fatigue/tiredness, fever, chills, nausea, new or worsened muscle pain, and new or worsening joint pain. These are assessed by the subject in a diary.

Solicited systemic reactions will be graded based on the criteria given in the US FDA Guidance for Industry 'Toxicity Grading Scale for Healthy Adult and Adolescent Volunteers Enrolled in Preventive Vaccine Clinical Trials'. The grades are Grade 1 (mild), Grade 2 (moderate), Grade 3 (severe), and Grade 4 (potentially life threatening). Fever is graded as mild (38.0 to 38.4°C), moderate (38.5 to 38.9°C), severe (39.0 to 40.0°C, and potentially life threatening (>40.0°C).

The solicited systemic reactions will be evaluated for each injection, i.e.

- First injection (Dose 1) up to day 7 (inclusive) after first injection (Group A, immunology subset of Group B)
- Second injection (Dose 2) up to day 7 (inclusive) after second injection (Dose 2) (immunology subset of Group B)
- Both intervals combined (immunology subset of Group B)

The intervals will start with the date and time of the injection.

Note: The interval 'first injection (Dose 1) up to day 7 after first injection' includes study day 1 to study day 7. This applies to the other intervals accordingly. All analyses are based on systemic reactions independent of their relatedness to IMP.

Analysis

Solicited systemic reactions will be analyzed in the same way as solicited local reactions (see Section 6.4.1).

6.4.3. Adverse events

Definition

For detailed information on adverse events see Section 10.3 of the protocol. Solicited AEs that are recorded from the subject diaries on the reactogenicity CRFs will not be reported as AEs unless the solicited AE meets criteria for SAE or begins after Day 8 or started before Day 8 and continues past Day 8.

Adverse events (AEs) will be coded using the Version MedDRA[®] 24.0 to get a system organ class (SOC) and preferred term (PT) for each AE.

A TEAE is defined as any AE with an onset after the first injection (Dose 1) (if the AE was absent before the first injection) or worsened after the first injection (Dose 1) (if the AE was present before the first injection (Dose 1)). AEs with an onset date more than 28 days after the last injection will be considered as treatment emergent only if

assessed as related to IMP by the investigator. AEs that cannot be determined to not be treatment emergent due to missing date or time will be defined as TEAE.

Note: To clarify the definition in the protocol, AEs with an onset date at the date of the first injection (Dose 1) will only be considered as treatment emergent if the AE occurred after the first injection (Dose 1). AEs with missing time and occurring on the day of Dose 1 or AEs with missing date will be analyzed as treatment emergent.

TEAEs will be evaluated for following time interval and groups:

- Up to 28 days after the first IMP injection (Group A and immunology subset of Group B)
- After the first IMP injection up to 28 days after the second IMP injection (immunology subset of Group B non-transplant)
- After the second IMP up to 28 days after the second IMP injection (immunology subset of Group B transplant)
- All TEAEs (Group A and immunology subset of Group B)

AEs are assigned to the time interval according to their start date and time. AEs with missing date will be assigned to each of the respective intervals if it cannot be ruled out, that it belongs to the time interval.

Adverse events of special interest (AESIs)

The following events will be reported as AESIs: myocarditis, pericarditis, anaphylaxis, thromboembolic events (e.g., deep vein thrombosis, stroke, myocardial infarction), immune thrombocytopenia and immune based neurologic events (e.g., optic neuropathy, Guillain-Barré syndrome). AESIs are recorded in the CRF.

AESIs and SAEs will be evaluated up to 26 weeks after the ICF was signed for all groups.

Analysis

The following TEAE types will be analyzed for Group A and the immunology subset of Group B:

- Any TEAE
- Related TEAE, i.e., suspected unexpected serious adverse reactions (SUSARs) which will be described in safety reports
- Any Grade ≥3 TEAE
- Any related Grade ≥3 TEAE
- Any treatment emergent serious adverse event (TESAE)
- Related TESAE
- TEAESI

- TEAEs linked to confirmed COVID-19 cases (TEAEs with preferred term = 'COVID-19')
- Deaths

The following AE types will be analyzed for all groups if applicable:

- Any AE
- Related AE
- Any Grade ≥3 AE
- Any related Grade ≥3 AE
- Any serious adverse event (SAE)
- Related SAE
- AESI
- Related AESI
- Any AEs linked to confirmed COVID-19 cases (AEs with preferred term = 'COVID-19')
- Deaths

Overall summary of TEAEs

For Group A and the immunology subset of Group B, the number and percentage of subjects reporting at least one TEAE and the number of TEAEs will be summarized for all TEAE types defined above overall.

For Group B, the number and percentage of subjects reporting at least one

- SAE
- AESIs

will be summarized.

For Group A and the immunology subset of Group B, the number and percentage of subjects reporting at least one TEAE and the number of TEAEs will be summarized by PT nested within SOC for each of the following AE types: Any TEAE, Related TEAE, Any TESAE, Related TESAE, TEAEs leading to treatment discontinuation, solicited TEAEs and fatal TEAE.

For Group B, the number and percentage of subjects reporting at least one TESAE will be summarized by PT nested within SOC.

If a SOC and PT is reported more than once for a subject, the subject will only be counted once for this SOC and PT at the worst grade level. All TEAE summary tables will be sorted alphabetically by SOC and PT within SOC.

TEAE by grade

For Group A and the immunology subset of Group B, the number and percentage of subjects with TEAEs and TESAEs will be summarized by worst grade by PT nested within SOC by time interval.

For Group B, the number and percentage of subjects with TESAEs will be summarized by worst grade by PT nested within SOC.

The worst grade will be counted if a TEAE is reported more than once by the same subject for this SOC and PT.

AEs

The number and percentage of subjects reporting at least one AE and the number of AEs will be summarized for the above defined AE types for all groups.

SAEs

The number and percentage of subjects reporting at least one SAE and the number of SAEs will be summarized by PT nested within SOC for each of the following AE types: Any SAE, Related SAE, fatal SAE and related fatal SAE.

Non-SAEs

The number and percentage of subjects reporting at least one non-SAE and the number of non-SAEs with >5% within any arm or reporting group will be summarized by PT nested within SOC.

AE listings

All TEAEs of subjects that withdrew due to AE, SAEs, and AESIs will be listed. The duration of an AE will be calculated in hours. If for an AE the time is missing then the duration will be calculated in days.

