10.3.1 Definition of AE and TEAE

- An AE is any untoward medical occurrence in a trial subject, temporally associated with the use of trial treatment, whether or not considered related to the IMP.
 NOTE: An AE can therefore be any unfavorable and unintended sign (including an abnormal laboratory finding that is clinically significant), symptom, or disease (new or exacerbated) temporally associated with the use of IMP.
- Events after signing ICF and before IMP administration will be handled as AEs (also called pre-existing conditions).
- A TEAE is defined as any AE with an onset after the first IMP injection or worsened after the first IMP injection (if the AE was present before the first administration of IMP). AEs with an onset date more than 28 d after the last administration of IMP will be considered as treatment-emergent only if assessed as related to IMP by the investigator.

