	Group B immunology subset and will receive one injection of Comirnaty [®] which could be potentially followed 3 to 7 months afterwards by a second injection of Comirnaty [®] . This group will be referred to as Group B transplants. Subjects not eligible during this period due to any medical reason (e.g., breakthrough infection causing investigational medicinal product delay decision from the investigator) will not receive the 4 th dose in this trial. Dose : 30 µg of Comirnaty [®] or BNT162b2s01 Dosing regimen: Group A: One (at Day 1) intramuscular injection with 30 µg of either Comirnaty or BNT162b2s01. Group B: Two (at Day 1 and Day 21) intramuscular injections with 30 µg of Comirnaty, except Group B transplant subjects. Group B transplant subjects: Two intramuscular injections of 30 µg of Comirnaty, with injection 2 administered 3 to 7 months after injection 1 (Day 1). The planned time points for injection of the investigational medicinal product for Groups A and B are provided in the Schedule of Activities in the protocol (Section 1.3)
	Administration route: Intramuscular
Treatment and study duration	In total, the planned trial duration for a subject in this trial is approximately 30 weeks (≤4 weeks of screening and ~26 weeks follow-up).
Planned number of subjects	The maximum number of subjects in Group A will be 90 (including up to 15 HIV-positive subjects) and in Group B will be 459 (including up to15 transplant subjects). A subset of Group B (n=129) will be asked to participate in an immunology subset evaluation.
Randomization and blinding	Subjects in Group A will be randomized in a 2:1 ratio to either BNT162b2s01 or Comirnaty [®] . All subjects in Group B will receive at least one injection of Comirnaty [®] . They will not be randomized. The study is open-label.

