6.1.2. Definitions and derivations

Unscheduled visits

Unscheduled visits will not be included in the summary tables but will be included in the listings.

Variables

Unless otherwise specified, **baseline** is defined as last value prior to first injection of IMP (Dose 1) given in this BNT162-14 trial on Day 1, including unscheduled visits.

Change from baseline will be calculated as follows:

• Change from baseline = post-baseline assessment value – baseline assessment value.

Duration [days] will be calculated as follows:

• Duration [days] = last observation date – first observation date + 1

Time from first injection (Dose 1) to first reaction will be calculated as follows: Time from first injection to first reaction [days] = first reaction date – date of first injection (Dose 1) + 1

Time from first reaction to last reaction will be calculated as follows:

Time from first to last reaction [days] = last reaction date – first reaction date + 1

Days since last injection will be calculated as follows:

Days since last injection = onset date of AE – date of last injection +1

For conversion of days to months or years the following rules will be applied:

- 1 month = 30.25 days
- 1 year = 365.25 days

Study Day and are defined as follows:

- Study day:
 - If study date < date of first injection (Dose 1), then study day = study date date of first injection
 - If study date >= date of first injection (Dose 1), then study day = study date date of first injection + 1

Fold rise will be calculated as follows:

• Fold rise = post-dose value / baseline value

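### For an unrelated event more than 28 days after Dose 1, treatment-emergent status depends on whether Dose 2 is given later, because the cut-off is tied to the last injection

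*SAP*

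**What the plan says.** SAP 6.4.3 starts treatment-emergence at the first injection and limits it at the other end: "AEs with an onset date more than 28 days after the last injection will be considered as treatment emergent only if" they are assessed as related to IMP. Protocol 10.3.1 has the same rule: "AEs with an onset date more than 28 d after the last administration of IMP will be considered as treatment-emergent only if assessed as related".

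For transplant subjects, SAP 1.2 places Dose 2 at 3 to 7 months after Dose 1 and does not guarantee it. "Subjects not eligible during this period due to any medical reason", with breakthrough infection as the example, do not receive it in this trial. Other Group B subjects are due Dose 2 at Visit 3 (study day 22±3), and Protocol 7.1.2 allows delays.

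SAP 6.4.3 reports transplant TEAEs for the 28 days after Dose 1, for the 28 days after Dose 2, and for all TEAEs without a time limit. The treatment-emergent types include SAEs, AESIs and COVID-19 events. For Group B as a whole it adds: "For Group B, the number and percentage of subjects reporting at least one TESAE will be summarized by PT nested within SOC". A table of TEAEs that led to stopping treatment is planned for Group A and the immunology subset. SAP 6.1.1 splits the Group B tables by transplant status.

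**The concern.** A 28-day limit counted from the last injection causes no difficulty when the doses are three weeks apart. With months between doses, the label given to an event is settled by what happens after it. Take an unrelated SAE at month 3. If the subject has Dose 2 at month 5, the SAE precedes the cut-off and is treatment-emergent. If Dose 2 is withheld, Dose 1 is the last injection and the SAE is not.

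The event can also influence that decision. A breakthrough infection that rules out Dose 2 is removed from the treatment-emergent outputs, while the same infection in a subject who goes on to Dose 2 is kept. At stake are the all-TEAE interval, the overall TEAE summary, and the treatment-emergent SAE, AESI and COVID-19 results. The discontinuation table is the sharpest case. It is restricted to TEAEs and has no counterpart based on all AEs, so an unrelated event beyond day 28 that stops Dose 2 cannot enter it.

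**Working it through.** The plan states no figure for this point and no hypothesis or sample size calculation (SAP 2 and 4), so there is nothing to reproduce. The check applies the rule as written.

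**Inputs**
- Transplant gap: 3 to 7 months (SAP 1.2), converted with "1 month = 30.25 days" (SAP 6.1.2): 3 × 30.25 = 90.75 d; 7 × 30.25 = 211.75 d.
- Other Group B: study day 22±3 (Protocol Tables 2 and 3), i.e. 18 to 24 days after Dose 1, nominally 21.
- Examples of permitted delay: 3, 5 and 12 weeks (Protocol 7.1.2).
- SAEs and AESIs are evaluated to 26 weeks after ICF signature (SAP 6.4.3); screening is Day -30 to -1 (Protocol 1.3).
- Transplant subjects: up to 15 (SAP 1.2).

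**Rule.** An unrelated event starting t days after Dose 1 is treatment-emergent if t − L ≤ 28. L is 0 if Dose 1 was the last injection and equals the gap if Dose 2 was given. The two answers differ when 28 < t < gap.

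**Example, Dose 2 at day 91.**
- t = 60 with Dose 2: 60 − 91 = −31, a TEAE. Without Dose 2: 60 − 0 = 60, not a TEAE.
- t = 10 or t = 28: a TEAE either way.

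**Discordant days**
- Transplant, 3 months: 90.75 − 28 = 62.75 d; 62.75/90.75 = 69% of the gap.
- Transplant, 7 months: 211.75 − 28 = 183.75 d; 183.75/211.75 = 87%.
- Non-transplant on schedule (18, 21 or 24 d): none.
- Non-transplant delayed: 21 + 21 = 42, days 29–41; 21 + 35 = 56, days 29–55; 21 + 84 = 105, days 29–104.

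**Width of the treatment-emergent window for an unrelated event**
- Transplant, no Dose 2: 28 d.
- Transplant, Dose 2 given: 90.75 + 28 = 118.75 d to 211.75 + 28 = 239.75 d by the definition alone.
- Non-transplant on schedule: 21 + 28 = 49 d.
- If the limit counted from ICF applies: 26 × 7 = 182 d, less 1 to 30 d of screening, so SAEs and AESIs count to at most 181 to 152 d after Dose 1.

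**Ratios for SAEs and AESIs with that limit**
- Dosed versus undosed transplant: 118.75/28 = 4.2, up to at most 181/28 = 6.5 (152/28 = 5.4 with consent at Day -30).
- Dosed transplant versus on-schedule non-transplant: 118.75/49 = 2.4, up to at most 181/49 = 3.7 (152/49 = 3.1).

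These are ratios of expected counts only under a constant event rate, which is an assumption.

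**Weight of one subject.** 1/15 = 6.7 percentage points in the transplant column.

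**After the fix.** Classification uses only injections given before onset, so the number of discordant days is 0.

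**The case against.** **The term is ambiguous.** SAP 6.1.2 computes days since last injection from AE onset. If that meant the final injection, between-dose events would generally come out negative, so the formula suggests the most recent injection before onset. Under that reading the problem disappears. Against it, SAP 6.3.2 uses first and last injection in the sense of the final dose, and the plain wording of Protocol 10.3.1 points the same way. The ambiguity stands and is itself a reason to define the term.

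**A reader might infer that these events vanish from the report.** They do not. SAP 6.4.3 also summarises AEs, SAEs, AESIs, COVID-19 AEs and deaths for all groups without a treatment-emergent condition. What those tables lack is a row for events leading to treatment discontinuation. The disposition summary in SAP 6.2 gives reasons for leaving the trial, which is a different thing.

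**A reader might infer that the primary results are affected.** They are not. In SAP 6.4 the 26-week SAE and AESI endpoints do not depend on treatment-emergent status, and the TEAE endpoint covers 28 days after each injection. The two 28-day transplant intervals match it.

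**A reader might extend the point to every between-dose event in Group B.** Events within 28 days of Dose 1 are TEAEs either way, and on-schedule non-transplant subjects have no discordant days.

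**A reader might take the widest windows, 239.75/28 = 8.6 and 239.75/49 = 4.9, as the inflation of TEAE counts generally.** That ignores the 26-week limit on SAEs and AESIs. It also ignores footnote k to Protocol Table 2: from Visit 5, unrelated AEs in transplant subjects are recorded only if they are SAEs, AESIs or COVID-19-linked.

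**No hypothesis is tested.** True; the harm is to descriptive safety tables.

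**Conclusion.** The point holds for unrelated events more than 28 days after Dose 1, in transplant subjects and in any Group B subject with a delayed Dose 2, if last injection means the final one received. Treatment-emergent status is then conditional on a later dosing decision that the event may have driven.

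For transplant subjects, 69% to 87% of the between-dose gap is exposed. For SAEs and AESIs, the window of a dosed transplant subject is about 4.2 to at most 6.5 times that of an undosed one, and about 2.4 to at most 3.7 times that of an on-schedule non-transplant subject. Those figures assume that the limit counted from ICF applies and, as ratios of counts, a constant event rate.

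The reach is small in numbers: up to 15 transplant subjects, plus delayed cases. The event types exposed are nevertheless the ones that matter most in this population. It should be corrected before the tables are produced, but it does not threaten the primary analysis.

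**What to change.** - **Definition.** In SAP 6.4.3, and in Protocol 10.3.1 or as an SAP clarification of it, state that an AE is treatment-emergent if it starts or worsens within 28 days after any IMP injection, counted from the most recent injection before onset, or later if assessed as related. The SAP already clarifies the protocol definition in this way for events on the day of Dose 1.
- **Interval.** For all transplant subjects, report the collected SAEs, AESIs and COVID-19 AEs from the 29th day after Dose 1 to Dose 2, or to the end of follow-up if Dose 2 is not given, as a separate interval.
- **Discontinuation table.** Base it on all AEs.

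The cost is one definition, one interval row and a wider base for one table. Trial conduct and data collection do not change. The downside is that some unrelated between-dose events move from the treatment-emergent tables to the interval row.
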